## 3. Study Design

VALID-II is a two-arm, non-randomised feasibility intervention study with a delayed intervention design. The study is conducted in two sequential phases rather than in parallel.

In the first phase, women diagnosed with GDM are allocated to a control group and receive standard care. During this phase, a subgroup of women and their informal support persons participate in an embedded ethnographic study. Findings from this qualitative work inform the co-creation of the intervention.

In the second phase, after a delay of approximately three months, a new group of women diagnosed with GDM is allocated to the intervention arm and receives the co-created intervention in addition to standard care. This delayed design was chosen to allow meaningful intervention development grounded in participants' lived experiences and to ensure cultural relevance.

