## 6. Recruitment and Study Procedures

At the first antenatal care visit, eligible women are informed about the study by trained study nurses or midwives. After providing written informed consent, participants complete a baseline questionnaire and are scheduled for a standard 75-g oral glucose tolerance test (OGTT) at gestational age 24–28 weeks.

OGTT procedures follow WHO and IADPSG diagnostic criteria. Women diagnosed with GDM are invited to participate in follow-up data collection and allocated to either the control or intervention group depending on study phase. Women without GDM continue routine care but contribute delivery and neonatal outcome data via medical records.

Women diagnosed with GDM complete additional questionnaires during pregnancy (32–40 weeks gestation) and at 8–12 weeks postpartum. Delivery and neonatal outcomes are abstracted from medical records.

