## 8. Outcome Measures

The primary outcomes relate to feasibility:

- Recruitment is defined as the proportion of eligible women who consent to participate.
- Retention is defined as the proportion of enrolled women who complete delivery and postpartum follow-up.
- Acceptability is assessed using both quantitative Likert-scale measures and qualitative ethnographic interviews.

Secondary outcomes include maternal outcomes (e.g., self-care agency, perceived social support, gestational weight gain, HbA1c, breastfeeding practices, postpartum depression) and neonatal outcomes (e.g., birth weight, gestational age, large for gestational age, macrosomia, neonatal hypoglycaemia).

All outcomes and measurement tools are predefined and aligned with the published protocol .

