## 9.3 Analysis of Secondary Outcomes

Secondary maternal and neonatal outcomes will be analysed descriptively and exploratorily. Continuous variables (e.g., birth weight, gestational age, self-care agency scores) will be summarised using means and standard deviations or medians and interquartile ranges, depending on distribution. Binary outcomes (e.g., large for gestational age, preterm birth) will be summarised as proportions.

For exploratory comparisons between intervention and control groups, regression models will be used where appropriate. Logistic regression will be applied to binary outcomes, and linear regression to continuous outcomes. Effect estimates will be presented as odds ratios or mean differences with 95% confidence intervals. No adjustment for multiple comparisons will be performed.

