## 9.4 Adjustment for Confounding

Because the study uses a non-randomised design, baseline characteristics will be examined for imbalance between groups. If clinically relevant imbalances are observed, adjusted analyses will be conducted including key covariates such as maternal age, body mass index, parity, and gestational age at diagnosis. Adjusted analyses are considered exploratory and intended to inform future trial design rather than establish causal inference.

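### Sections 9.3 and 9.4 do not prespecify adjusting self-care agency and perceived social support for the woman's own baseline score; adjustment of any kind waits on an undefined imbalance check

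*Combined protocol and SAP*

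**What the plan says.** Section 3 describes the design: "VALID-II is a two-arm, non-randomised feasibility intervention study with a delayed intervention design". Controls are enrolled first. About three months later "a new group of women diagnosed with GDM is allocated to the intervention arm". The contrast is therefore between different women in different calendar periods.

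Section 8 lists the secondary maternal outcomes as "self-care agency, perceived social support, gestational weight gain, HbA1c, breastfeeding practices, postpartum depression". Section 6 gives the measurement times. After consent, "participants complete a baseline questionnaire and are scheduled for a standard 75-g oral glucose tolerance test (OGTT) at gestational age 24–28 weeks". Later, "Women diagnosed with GDM complete additional questionnaires during pregnancy (32–40 weeks gestation) and at 8–12 weeks postpartum". The content of the baseline questionnaire is not given, and Section 8 refers to a published protocol for the measurement tools.

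On analysis, Section 9.3 says "Logistic regression will be applied to binary outcomes, and linear regression to continuous outcomes", with mean differences and 95% confidence intervals, and names self-care agency scores among the continuous variables. Section 9.4 provides for adjustment only where the groups are seen to differ at baseline to a clinically relevant degree. In that case "adjusted analyses will be conducted including key covariates such as maternal age, body mass index, parity, and gestational age at diagnosis". The degree is not defined. Neither a baseline-score covariate nor a change-from-baseline analysis is mentioned anywhere.

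**The concern.** Self-care agency and perceived social support are the scales closest to what a self-care and informal support intervention tries to change. If the women in the second phase already scored higher or lower before the intervention, part of that difference will appear in the follow-up comparison as if it were an effect. Adjusting for age, BMI, parity and gestational age at diagnosis removes it only so far as those variables account for it.

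The conditional rule adds two problems. With no threshold, whether to adjust, and for what, is settled after the data are seen. And if the groups look balanced, the model leaves out a covariate that would have narrowed the interval anyway.

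The exploratory label does not remove the stake. Section 2 says the purpose of these analyses is to supply effect sizes and variances for planning a later trial, and Section 9.1 puts the weight on estimation and confidence intervals. Both planning quantities depend on how the baseline score is handled.

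**Working it through.** **What can be reproduced.** Nothing: the documents state no sample size, SD, target difference, power or baseline-to-follow-up correlation for these scales. The figures below are illustrations under stated assumptions.

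**Inputs from the documents.** Two non-randomised successive groups (Section 3); a questionnaire completed before the OGTT, hence before GDM diagnosis and before the intervention (Section 6); linear regression giving a mean difference (Section 9.3); two-sided 0.05 (Section 9.1).

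**Assumed inputs.** Correlation r between a woman's baseline and follow-up score of 0.3, 0.5 or 0.7; equal SDs at the two times and in both groups; a baseline gap g of 0.2 SD between phases; for the sample-size column only, a true difference of 0.5 SD and 80% power.

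**Formulas.**
- Residual variance with the baseline score in the model, relative to without it: 1 − r².
- Standard error (and interval width) ratio: √(1 − r²).
- Part of a baseline gap left in the unadjusted follow-up difference: about r × g.
- Women per arm: 2 × (1.96 + 0.84)² × (1 − r²) / 0.5², which is 63 with no baseline score in the model.

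| Assumed r | 1 − r² | Variance cut | √(1 − r²) | SE cut | r × 0.2 SD | n per arm (63 unadjusted) |
|---|---|---|---|---|---|---|
| 0.3 | 0.91 | 9% | 0.954 | 5% | 0.06 SD | 58 |
| 0.5 | 0.75 | 25% | 0.866 | 13% | 0.10 SD | 48 |
| 0.7 | 0.51 | 49% | 0.714 | 29% | 0.14 SD | 33 |

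Read the other way, leaving the score out widens the interval by 1/0.954 to 1/0.714, that is by about 5% to 40%.

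**Limits of the illustration.** If the named covariates are also in the model, r stands for the correlation that remains after them. The r × g figure treats the gap as one that regresses toward the mean. If it is instead a stable difference between the two cohorts, the whole 0.2 SD carries into follow-up. Adjustment for one imperfectly measured baseline then takes out only the r × g part, leaving 0.20 − 0.14 = 0.06 SD at r = 0.7 and 0.20 − 0.06 = 0.14 SD at r = 0.3.

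**The case against.** The strongest objection is that the baseline scores may not exist. A reader might infer that every woman has a baseline self-care and support score which the analysis ignores. The documents do not support that. Section 6 says only that a baseline questionnaire is completed, by all consenting women and before GDM is known; the questionnaires for women with GDM are described as additional and come from 32 weeks onward. If the scales are first given then, there is no score to adjust for and no precision is lost by this choice. This objection stands, and it makes the point conditional.

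A reader might also infer that the plan rules baseline adjustment out. It does not. The covariate list in Section 9.4 is open, and baseline characteristics are to be examined, so a baseline score could enter. The accurate statement is that it is not prespecified. That still matters: Section 9.1 fixes the SAP only before intervention-group data collection is complete, so an open list behind an undefined trigger leaves a real choice for later.

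It would be too strong to say that the named covariates predict these scores poorly, or that the baseline score is the main confounder. The documents give no figures on either. The argument needs only a correlation above zero. With the baseline taken at an early antenatal visit and follow-up in late pregnancy or postpartum, that correlation could be low.

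Nor would it be justified to insist that scales without a baseline be reported only descriptively. A covariate-adjusted contrast with its limitation stated is legitimate exploratory reporting under Sections 9.3 and 9.4.

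Finally, Section 9.4 disclaims causal inference. That limits the consequence but does not touch the planning use set out in Section 2.

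**Conclusion.** The concern holds in a limited form and is a cheap improvement. Sections 9.3 and 9.4 do not prespecify the woman's own baseline score for self-care agency or perceived social support, and any adjustment rests on an undefined imbalance check between non-randomised successive groups. For any scale already in the baseline questionnaire, always including the baseline score is better than the conditional rule.

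The size depends on a correlation that the documents do not give. Across an assumed 0.3 to 0.7 the gain runs from slight (SE 5% smaller) to substantial (SE 29% smaller), and an assumed 0.2 SD baseline gap would put roughly 0.06 to 0.14 SD into the unadjusted difference.

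Baseline adjustment does not remove calendar-time or other unmeasured differences between phases, so the contrast stays non-randomised and exploratory. Recruitment, retention and acceptability are not affected.

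**What to change.** In Sections 9.3 and 9.4:

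- State which of the outcome scales the pre-OGTT baseline questionnaire contains.
- For each of those scales, make the reported mean difference a linear regression of the follow-up score on group, baseline score and the named covariates, whatever imbalance is seen. Do this at each follow-up time at which the scale is given.
- Give a simple rule for missing baseline scores. One that fits the no-imputation position of Section 9.5 is to fit the model in women with both scores, report by group how many drop out, and show the estimate without the baseline score in all available women beside it.
- For scales not asked at baseline, keep the covariate-adjusted exploratory contrast and state with the result that prior differences in the score are not controlled.
- Report the follow-up SD, the residual SD and the observed baseline-to-follow-up correlation, so that the later trial can be planned on the right variance.

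The cost is SAP wording; no new data are needed for scales already collected. The downside is that women with a missing baseline score have to be handled explicitly.

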### 9.5 Missing Data

The extent and patterns of missing data will be described for all outcomes. Given the feasibility focus of the study, no formal imputation of missing data is planned. Analyses will be based on available data, and the potential impact of missingness will be discussed qualitatively.

### 9.6 Qualitative Data Analysis

Qualitative data from ethnographic interviews and fieldnotes will be transcribed verbatim and analysed using a content analysis approach. Coding will be performed iteratively, and themes related to feasibility, acceptability, self-care practices, and informal support will be identified. Qualitative findings will be used to contextualise quantitative results rather than to generate statistically generalisable conclusions.

## 10. Data Management

All quantitative data are collected and stored using REDCap on secure servers at Thai Binh University of Medicine and Pharmacy. Data exports for analysis will be performed using Stata, SPSS, or R. Access to identifiable data is restricted to authorised study personnel.

## 11. Ethics and Trial Status

The study has received ethical approval from the Ethics Council in Biomedical Research in Thai Binh (IRB – VN01.009). All participants provide written informed consent prior to participation. The trial is registered at ClinicalTrials.gov (NCT05744856) and is currently ongoing.
